- If the following grade 3 or 4 toxicities occur as a result of chemoembolization, no additional session will be performed (but FOLFOX will be continued).

- Arteritis
- Grade 3 or 4 hepatic impairment
- Local ischemic and septic manifestations (cholecystitis, hepatic infarction, hepatic abscess, digestive hemorrhage) of grade 3 or 4
- Grade 3 or 4 renal insufficiency
- **The interval between chemoembolization sessions may be extended to allow for recovery of liver function.**
- No dose adjustment of irinotecan is planned for chemoembolization sessions.
- In case of hematological toxicity, FOLFOX dose adjustment rules **will be applied and chemoembolization will be continued.**

In case of doubt, do not hesitate to ask for advice from the study's referring radiologist, [name], through the FFCD.

VII. PATIENT MONITORING DURING TREATMENT AND AFTER WITHDRAWAL OF TREATMENT

Monitoring during treatment:

- **Before each cycle of FOLFOX:**
 - Complete clinical examination including: weight, vital signs, WHO, pain assessment (VAS)
 - Biological check-up: CBC/platelets
 - Adverse event evaluations according to NCI CTC version 4.0
- **Before each chemoembolization session**
 - Complete clinical examination including: weight, vital signs, WHO, pain assessment (VAS)
 - Biological workup consisting of measurements of hematological, nephrological and hepatic parameters: CBC/platelets, blood ionogram, creatinine, albumin, transaminases (AST, ALT), alkaline phosphatases (ALP), total and conjugated bilirubin, PT
 - Adverse event evaluations according to NCI CTC version 4.0

CEA and CA 19-9 assays, as well as thoracoabdomino-pelvic CT and liver MRI will be performed at an initial evaluation between D63 and D70 and then every 2 months after the start of treatment.

For patients participating in the associated 'lipid' translational study, please remember to perform the fasting sample and then technician the sample.

After the chemoembolization treatment period:

All patients will receive chemotherapy with FOLFOX every 2 weeks according to the usual regimen until progression or unacceptable toxicity.

VIII. STOP PROCESSING THE STUDY

The processing of the study will be stopped in case of:

- Investigator's decision
- Major toxicity requiring discontinuation of treatment (despite protocol adaptations)
- Serious or unexpected event requiring discontinuation of protocol treatment
- Progression of the disease
- Patient refusal or withdrawal of consent

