In all cases of treatment discontinuation, the patient remains in the analysis for intention-to-treat and overall survival, and for 30 days after the last study treatment for toxicity.

There is no exclusion period for a subsequent therapeutic trial.

IX. CENTRALIZED READING OF CT SCANS AND MRI

Responses will be evaluated according to RECIST version 1.1 criteria (Appendix 3) and will be reviewed by a panel of independent radiologists according to RECIST version 1.1 criteria and EASL criteria (Appendix 4).

Don't forget to keep the CDs and the report of the CT and MRI evaluation in the patient's file; the FFCD CRA will make a copy of these imaging assessments to centralize them at the CRGA on the 'FFCD Images' platform using a secure transmission via the company ETIAM.

X. MANAGEMENT OF SERIOUS ADVERSE EVENTS (SIA)

Safety will be assessed by evaluating the general, clinical and biological status of patients at the time of scheduled visits and by collecting events occurring between visits. Toxicities will be assessed using the NCI-CTC Toxicity Scale version 4.0 (Appendix 5).

X.1 Definitions

Adverse Event (AE)

An adverse event is a harmful occurrence in a person who is a subject of biomedical research, whether or not the occurrence is related to the research or the product being investigated. All adverse events will be recorded in the observation book on the pages provided.

Serious Adverse Event (SAE)

A serious adverse event is any event that meets at least one of the following criteria:

- Resulting in death,
- Life-threatening,
- Leading to hospitalization or prolonged hospitalization,
- Causing permanent disability or severe temporary incapacity,
- Causing a birth defect, fetal malformation or abortion,
- Medically significant (examples: overdoses, second cancers, pregnancies and new developments may be considered medically significant)

Pregnancy is an exclusion criterion in this trial.

However, if a pregnancy is discovered after inclusion, the patient must be excluded from the trial. The sponsor should be informed immediately via the Serious Adverse Event Reporting Form (no severity criteria should be checked). The patient should be followed until the outcome of the pregnancy and this outcome, whatever it may be, should be reported to the sponsor.

Hospitalizations included in the protocol will not be considered an SAE.

Undesirable Effect

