The primary endpoint will be the proportion of patients alive without progression (death will be considered as progression) at 9 months after the start of treatment according to RECIST V1.1 criteria, as assessed by the investigator.

Progression-free survival time will be defined as the time interval between the date of inclusion and the date of progression or death (regardless of cause). For patients alive without progression, the time interval between the date of inclusion and the date of last morphological evaluation will be taken.

XII.2.2 Secondary Criteria

The secondary endpoints will be:

- Tolerance to the treatment
- Response rate according to RECIST v1.1 criteria at 9 months (according to the investigator)
- Response rate according to EASL criteria (assessed by centralized review) at 9 months
- Hepatic progression-free survival according to RECIST v1.1 criteria at 9 months
- Overall survival
- Progression-free survival
- The rate of secondary resections
- Changes in tumor marker levels

Liver progression-free survival will be defined as the time interval between the date of inclusion and the date of liver progression as assessed by the investigator's RECIST V1.1 criteria or death (regardless of cause) or the date of the last morphological assessment for patients alive without progression.

Overall survival will be defined as the time interval between the date of inclusion and the date of death regardless of the cause of death or the date of last news for living patients.

Tolerance to treatment will be assessed by:

- duration of treatment, doses received, dose reductions and deferrals
- Toxicities collected at each monthly visit, and described according to NCI-CTC version 4.0 criteria; Grade 3, Grade 4 and Grade 5 toxicities will be reviewed
- the number and description of SAEs

Changes in tumor marker levels (CEA and CA 19-9) will be assessed throughout the study.

XII.3 Calculation of the number of subjects needed

A 1-step Fleming design will be used, with a one-sided α risk of 5% and a power (1- β) of 90%.

The assumptions are:

- H0: A proportion of patients living without progression of 55% during the first 9 months is uninteresting;
- H1: A proportion of patients living without progression of more than 55% during the first 9 months would show the interest of the treatment; a proportion of 75% is hoped for.

Total number: **48 evaluable patients**

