4.3 Justification of the number of subjects needed

A 1-step Fleming design was used, with a one-sided α risk of 5% and a power ($1-\beta$) of 90%.

The clinical assumptions made were:

H_0 : A 55% progression-free live proportion during the first 9 months is unattractive;

H_1 : A proportion of patients alive without progression of more than 55% during the first 9 months would show the interest of the treatment; a proportion of 75% is hoped for.

48 evaluable patients were required. Taking into account a 20% rate of patients lost to follow-up or not evaluable, 58 patients were to be included.

The decision rules are as follows: of the 48 evaluable patients

- If 32 or fewer patients are alive without progression, then the treatment is considered ineffective
- If 33 or more patients are alive without progression, then the treatment is considered effective

The decision rule will be adjusted based on the actual number of evaluable patients.

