7.4.6.1 Definition of progression-free survival

It is defined as the time interval between the date of inclusion and the date of 1^{ère} radiological progression or the date of death (from any cause). Patients alive and without progression will be censored at the date of last news.

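### Protocol VII does not require tumour imaging after treatment stops without progression, although the 9-month endpoint and PFS run on past that point

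*Protocol*

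**What the plan says.** **Imaging schedule.** The title of Protocol VII contains "MONITORING DURING TREATMENT" and goes on to name the period after withdrawal. The section has two parts. The on-treatment part holds the only imaging calendar: CT, liver MRI and tumour markers are "performed at an initial evaluation between D63 and D70 and then every 2 months after the start of treatment". The part on the period after chemoembolization says only that FOLFOX continues. The calendar has no stated end.

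**Stopping.** Protocol VIII lets treatment end without progression (investigator decision, toxicity, serious event, refusal). It then says that "the patient remains in the analysis for intention-to-treat and overall survival, and for 30 days after the last study treatment for toxicity". Tumour assessment is not mentioned.

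**Endpoints.** The primary endpoint is investigator-assessed RECIST status at 9 months (Protocol XII.2.1, SAP 7.3.1). For PFS, SAP 7.4.6.1 states: "Patients alive and without progression will be censored at the date of last news". SAP 7.4.5.1 does the same for hepatic PFS. SAP 6.2 lets last news be any examination, treatment or visit. Protocol XII.2.1 instead takes the last morphological evaluation for a patient alive without progression.

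**Evaluability.** One assessment within the 9 months is enough, given a chemoembolization and one chemotherapy cycle (SAP 5.1.2).

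**The concern.** The endpoints follow a patient beyond the end of treatment, and the written imaging schedule may not. A site that reads the calendar as on-treatment only can stop scanning a patient who leaves for toxicity at month 4 and still comply with the protocol. That patient counts among the evaluable, yet the 9-month status is never measured. For PFS under the SAP, later visits without a scan add time that counts as progression-free.

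Two results are at stake. The decision rests on 33 or more successes in 48, so a few patients of undetermined status can settle it. The PFS and hepatic PFS curves can also read too high. A scan that was not done cannot be recovered at analysis.

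**Working it through.** **1. The plan's own figures.** Null: "A proportion of patients living without progression of 55% during the first 9 months is uninteresting". Target: "a proportion of 75% is hoped for". One-sided α is 5% and power 90%.
- n = [(1.645·√(0.55·0.45) + 1.282·√(0.75·0.25)) / 0.20]² = 47.14, rounded up to 48. SAP 4.3 agrees: "48 evaluable patients were required".
- Cut-off: 48·0.55 + 1.645·√(48·0.55·0.45) = 32.07, so 33 or more.
- Exact binomial: P(X ≥ 33 | 0.55) = 3.69%; P(X ≥ 33 | 0.75) = 87.7%.
- 48·1.2 = 57.6, so 58 included.

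**2. How sensitive the rule is.** If k true failures among the 48 are recorded as successes, the chance of passing under the null is P(X ≥ 33 − k | 0.55): 3.7% for k = 0, 6.8% for 1, 11.7% for 2, 18.5% for 3.

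**3. How many patients could be affected.** The documents give no stopping rate, so these are assumptions: in the absence of progression, s = 15%, 25% or 35% stop by 9 months; no scans after stopping; constant hazards; 55% true 9-month PFS; median survival after progression 12 to 18 months.
- Progression hazard λ = −ln(0.55)/9 = 0.0664 per month. Stopping hazard μ = −ln(1 − s)/9.
- A: stopped before month 8 without progression = μ/(λ+μ)·[1 − exp(−8(λ+μ))].
- B: progression between stopping and month 9 = 0.45 − λ/(λ+μ)·[1 − exp(−9(λ+μ))].
- C: as B and still alive at 9 months = ∫₀⁹ λe^(−λt)(1 − e^(−μt))e^(−δ(9−t)) dt, with δ = ln 2/12 or ln 2/18. Deaths are excluded because they count as failures without a scan.
- D: type I error if all of C were scored as successes = P(X ≥ 33 | 0.55 + C).

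| s | A (of 48) | B (of 48) | C (of 48) | D |
|---|---|---|---|---|
| 15% | 10.5% (5.0) | 3.1% (1.5) | 1.25–1.33 | 7.7–8.0% |
| 25% | 17.7% (8.5) | 5.3% (2.6) | 2.12–2.26 | 12.0–12.8% |
| 35% | 25.1% (12.0) | 7.7% (3.7) | 3.04–3.23 | 18.3–19.8% |

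In round terms, C is about 1.3 to 3.1 of 48 and D about 8 to 19%. The model includes patients who stop before the first scan at D63–D70. Without any assessment they would not be evaluable, so C is somewhat high.

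**4. PFS.** True 12-month PFS is 0.55^(12/9) = 0.45. With last-news censoring, a patient with unseen progression stays event-free until death, and the curve reads about 0.49, 0.52 and 0.54 for the three values of s. Censoring everyone at treatment stop returns 0.45. Censoring the living at the last scan while entering later deaths at their date leaves roughly 0.47 to 0.52.

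**5. Scoring unscanned patients as failures.** Under 75%, the share off treatment before month 8 but truly progression-free at 9 months is 0.75·[1 − exp(−8μ)] = 10.1%, 16.9% or 23.9%. If none is scanned and all count as failures, P(X ≥ 33) falls from 87.7% to about 35%, 9% or 1%. A scoring rule cannot replace the scans.

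**The case against.** The best defence is that imaging was always meant to continue. The calendar runs from the start of treatment, not from cycles, and has no end date. The section title covers withdrawal. SAP 7.4.9.1 follows the markers, which Protocol VII schedules in the same sentence as the scans, from inclusion to progression. Protocol XII.6 has the panel confirm dates of recurrence. This stands as evidence of intent. It rules out the inference that observation ends at treatment stop. It does not give sites an instruction, and the calendar still sits under the on-treatment sub-heading.

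Three other stronger readings are tempting, and the documents do not support them:
- **Unscanned patients are counted as successes.** SAP 7.3.1 covers late scans, late progression and earlier progression. It is silent on an evaluable patient with no later scan, and SAP 6.3 does not replace missing data. The scoring is open.
- **Five to twelve of 48 are misclassified.** That is column A, and most of those patients would truly be progression-free at 9 months.
- **The plan as a whole credits unscanned time.** The SAP does. Protocol XII.2.1 does not for living patients, so most of the PFS inflation comes from the SAP's censoring date.

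The stopping rate may also be lower than assumed. Protocol VI gives toxicities that end oxaliplatin alone, or further chemoembolization, while other treatment goes on. Secondary resection is not among the stopping reasons in Protocol VIII. Some scans will be done outside the schedule, so no scans at all is the extreme case.

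**Conclusion.** The gap is real but limited. Imaging after a stop without progression is not explicitly required, although the 9-month endpoint and PFS need it. The two documents censor PFS differently, and the SAP has no 9-month rule for an evaluable patient whose scans end early.

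On the stated assumptions, about 1.3 to 3.1 of 48 patients would be alive at 9 months with unseen progression. A type I error of about 8 to 19% instead of 3.7% follows only if they are all scored as successes. The 12-month PFS of 0.49 to 0.54 instead of 0.45 belongs to last-news censoring. These figures show what is possible under an assumed stopping rate and no later scans; they do not estimate bias in this trial. The text should be amended, because a missing 9-month scan cannot be repaired at analysis.

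**What to change.** 1. **Protocol VII:** state that patients who stop protocol treatment without progression continue the same two-monthly CT, liver MRI and marker evaluations until progression, death or withdrawal of consent.
2. **Protocol VIII:** state that they remain in the analyses of the 9-month endpoint and PFS.
3. **SAP 7.4.5.1, 7.4.6.1 and 7.6.1:** censor patients alive without progression at the last morphological evaluation, as Protocol XII.2.1 does.
4. **SAP 7.3.1:** add a rule for evaluable patients with no scan at or after the 9-month window. Count them as failures, at least in a sensitivity analysis, and report their number. If follow-up is already complete, items 3 and 4 can still be done before the database is frozen.

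The cost is a short protocol amendment, an SAP revision and some further CT and MRI in patients off treatment. No new type of procedure is needed. The 48 evaluable patients, the cut-off of 33 and the 58 included stay as they are.

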Any noxious and undesired response to an investigational drug at any dose or to any investigational component. The adverse reaction is serious if it meets the severity criteria (see above).

Unexpected Serious Adverse Effect

An unexpected serious adverse reaction is an event that is not mentioned, or is different in nature, intensity, or evolution from the product reference document.

In this essay the reference documents will be:

- For irinotecan-loaded beads (DEBIRI): the Investigator's Brochure
- For FOLFOX: the Summaries of Product Characteristics for oxaliplatin, 5-fluorouracil, folinic acid (Appendix 7)

The versions of the PCRs used for the definition of expected or unexpected will be the latest available on the anniversary date of the start of the trial.

X.2 Course of action

The investigator informs the sponsor of all Serious Adverse Events (Expected and Unexpected), whether or not attributable to the research, that occur during treatment and within 30 days of the last treatment administration.

All Delayed Serious Adverse Events (occurring after this 30-day period) considered reasonably related to the protocol treatment(s) or research should be reported without time limitation.

The report is made by faxing the "notification of a serious adverse event" form (Appendix 8), documented as precisely as possible, dated and signed, within 24 working hours of their discovery to the FFCD's Randomization Management Analysis Center (CRGA): by fax to [name].

Modalities and duration of follow-up of individuals following the occurrence of adverse events.

The investigator is responsible for appropriate medical follow-up of patients until resolution or stabilization of the effect or until the patient's death. This may sometimes mean that this follow-up extends beyond the patient's discharge from the trial.

He/she transmits the additional information to the sponsor using an SAE reporting form (checking the Follow-up No. X box to specify that it is a follow-up report and not an initial report) within 24 hours of obtaining it. It also forwards the latest follow-up to the resolution or stabilization of the SAE.

He keeps the documents concerning the suspected adverse reaction in order to allow, if necessary, to complete the information previously transmitted.

XI. ANCILLARY STUDIES

- **Associated 'lipid' study**

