Taking into account a rate of 20% of patients lost to follow-up or not evaluable, **58 patients should be included**.

At the end of recruitment:

During analysis:

- if 32 or fewer patients are alive without progression, then the treatment is considered ineffective
- if 33 or more patients are alive without progression, then the treatment is considered effective

The decision rule will be adjusted based on the actual number of evaluable patients.

XII.4 Statistical analysis plan

Analysis Populations:

Patients included in the study will be described on an intention-to-treat (ITT) basis as well as patients not evaluable for the primary endpoint.

A patient is considered evaluable if he or she has had chemoembolization and received at least one cycle of chemotherapy and for whom we have at least one evaluation during the 9 months of follow-up.

All efficacy analyses will be performed on a modified intention-to-treat basis (evaluable patients) included in the study regardless of eligibility criteria and treatment received.

Tolerability population: the ITT population that received at least one dose of the treatments.

In all cases of discontinuation, the patient remains in the intention-to-treat analysis. There is no exclusion period for a subsequent therapeutic trial.

Key analyses:

A statistical analysis plan will be written prior to freezing the database.

The description of clinical and medical variables will be done using percentages (95% confidence interval) for qualitative variables and mean (standard deviation) and median (Min-Max) as well as inter-quartile range (Q1-Q3) for quantitative analysis.

Survivals and times will be estimated by the Kaplan Meier (KM) method. They will be described by medians and rates at different time points with their 95% confidence intervals.

Median follow-up time will be calculated using the reverse Kaplan Meir method.

The time to onset of grade 3/4/5 toxicity will be estimated using the Kaplan Meier method.

Exploratory Analyses:

- research into factors predictive of progression-free survival and/or overall survival

XII.5 Independent Committee Supervisory Committee

An independent committee composed of 1 clinician / 1 methodologist / 1 pharmacovigilant expert will be formed before the start of the trial.

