6.5 Statistics

The confidence intervals provided will be two-sided 95% confidence intervals except for the primary endpoint where the calculated confidence interval will be a one-sided 95% confidence interval.

Quantitative data will be described using the following descriptive statistics: number, mean, standard deviation, median, first and third quartile, and minimum and maximum. These statistics will be considered the usual statistics for the analysis of quantitative variables. Quantitative variables can be categorized using their median or a cut-off known from the medical literature.

Categorical variables will be summarized, using the following descriptive statistics: the number, frequencies and percentages for each level of the variable. These statistics will be considered as the usual statistics for the analysis of categorical variables.

When necessary, the 95% confidence intervals for the proportions can be calculated from the exact binomial distribution.

Survival data will be estimated and plotted using the Kaplan Meier method (Kaplan and Meier, 1958). They will be described by the median and rates calculated at different time points with their two-sided 95% confidence intervals. The confidence intervals for the rates will be constructed from the Greenwood variance calculated using the log-log transformation.

The median follow-up time will be estimated by the reverse Kaplan-Meier method (Shemper, 1996).

As an exploratory measure, for the uni and multivariate analyses, the hazard ratios will be estimated using a Cox model (Cox, 1984). The hypothesis of proportionality of the rates will be tested using the graphical representation and the test based on Schöenfeld's residuals (Grambsch, 1994); the linearity of the effect of the continuous variables on the risk will be evaluated from the graphical representation of the martingale residuals. Confidence intervals for the coefficient estimates of the Cox models will be calculated using the Wald method.

7 Statistical analysis

	Population ITT	Population ITTm	Tolerance population	Population Per protocol
Description of Baseline				
Eligibility criteria for inclusion	X	X		X
Demographic characteristics	X	X		X
Clinical characteristics at inclusion	X	X		X
Biological characteristics at inclusion	X	X		X
Characteristics related to the disease	X	X		X
Median follow-up time	X	X		X
Main criterion				
Progression-free survival rate at 9 months	X	X		X
Secondary criteria				

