7.5.3 Toxici

Toxicities during treatment will be described according to NCI-CTC version 4.0 criteria by:

- The number of patients and toxicities by maximum grade and type;
- The number and percentage of patients with at least one toxicity across all courses by grade;
- The number and percentage of patients with at least one maximum grade 3-4-5 toxicity over all courses or at least one maximum grade 1-2 toxicity;

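### Kaplan-Meier for time to grade 3/4/5 toxicity (Protocol XII.4) has no competing-event handling, so its complement overstates the proportion of patients affected if it is read that way

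*Protocol*

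**What the plan says.** Protocol XII.4, under the key analyses: "The time to onset of grade 3/4/5 toxicity will be estimated using the Kaplan Meier method". The same list says that survivals and times are summarised by medians and by rates at time points, with 95% confidence intervals. It gives no time origin, censoring rule or competing event for the toxicity analysis, and does not say that the event is the first such toxicity.

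Three other parts of the protocol fix how long toxicity can be observed.
- Section VII, on duration of treatment: "All patients will receive chemotherapy with FOLFOX every 2 weeks according to the usual regimen until progression or unacceptable toxicity". Section VIII adds investigator decision, refusal or withdrawal of consent, and serious events as reasons to stop.
- Section VIII keeps a patient who has stopped in the analysis "and for 30 days after the last study treatment for toxicity".
- Section X.2 makes one exception: a serious event that arises later, if judged related to the treatment or the research, stays reportable with no limit in time.

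The SAP has no time-to-toxicity analysis. Section 6.5 describes Kaplan-Meier for survival outcomes only: "Survival data will be estimated and plotted using the Kaplan Meier method". Section 7.5.3 summarises toxicity by counts and percentages, including "The number and percentage of patients with at least one maximum grade 3-4-5 toxicity over all courses". Neither document mentions a competing-risk estimator.

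**The concern.** Kaplan-Meier gives each patient one of two outcomes: event or censored. A patient who progresses, stops treatment and completes the 30-day window without a grade 3 to 5 toxicity has had no event. Nor has a patient who dies of cancer without one. Both must be censored, and the estimator then treats them as if they would go on to have toxicity at the rate of patients still under treatment. Its complement (1-KM) describes toxicity if nobody progressed, stopped or died of other causes. It does not give the proportion of treated patients affected.

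What is at stake is the reading of tolerance, the first-listed secondary objective. The synopsis motivates the regimen by the toxicity of intravenous triple therapy. A single-arm trial has no control toxicity rate, so its figure will be set against outside figures. An inflated cumulative rate would distort that comparison and would not match the crude percentages of SAP 7.5.3.

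**Working it through.** The plan states no toxicity incidence, so there is no figure of its own to reproduce.

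**Direction.** Each Aalen-Johansen increment is the toxicity hazard times the proportion still free of both toxicity and the competing event. Each 1-KM increment is the same hazard times the Kaplan-Meier proportion free of toxicity, which is at least as large. So 1-KM cannot fall below the cumulative incidence (CIF).

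**Inputs from the documents**
- Progression-free at 9 months: 55% (H0) and 75% (H1), Protocol XII.3.
- Toxicity window after stopping: 30 days, Protocol VIII, taken as w = 1 month after progression.
- n = 58, the planned inclusions.

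**Assumptions**
- Toxicity is independent of progression, and progression or death has a constant hazard.
- Case A: constant toxicity hazard, 40% to 70% affected by 6 months (as 1-KM).
- Case B: the hazard after month 2 is one tenth of the hazard before it, with 1-KM of 40% to 70% at 9 months.

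**Case A formulas**
- λ1 = -ln(1 - tox6)/6; λ2 = -ln(PFS9)/9.
- 1-KM(t) = 1 - exp(-λ1 t).
- CIF(t) = 1 - exp(-λ1 w) + exp(-λ1 w) × λ1/(λ1+λ2) × [1 - exp(-(λ1+λ2)(t - w))].
- SE = sqrt(CIF(1 - CIF)/58).

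Example with 60% by 6 months and PFS 75%:
- λ1 = 0.15272 and λ2 = 0.03196.
- 1-KM(9) = 74.7%.
- CIF(9) = 0.1416 + 0.8584 × 0.8269 × 0.7718 = 68.9%.
- Excess 5.8 points; SE 6.1 points; ratio 0.95.

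Results at 9 months (differences taken before rounding):

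| Toxicity by 6 months | 1-KM | CIF, PFS 75% | Excess (SE) | CIF, PFS 55% | Excess (SE) |
|---|---|---|---|---|---|
| 40% | 53.5% | 48.8% | 4.8 (0.72) | 44.4% | 9.1 (1.40) |
| 60% | 74.7% | 68.9% | 5.8 (0.95) | 63.6% | 11.1 (1.75) |
| 70% | 83.6% | 77.8% | 5.8 (1.06) | 72.4% | 11.2 (1.90) |

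At 6 months the same formula gives an excess of 2.2 to 6.5 points (0.35 to 1.0 SE).

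**Case B formulas.** The hazard is a up to month 2 and b = a/10 after it. The cumulative hazard at 9 months is 2a + 7b = 2.7a, so a = -ln(1 - q)/2.7, where q is 1-KM at 9 months.

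CIF(9) = [1 - exp(-a)] + exp(-a) × a/(a+λ2) × [1 - exp(-(a+λ2))] + exp(-2a-λ2) × b/(b+λ2) × [1 - exp(-7(b+λ2))].

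Example with q = 60% and PFS 55%: a = 0.3394, λ2 = 0.06643, and CIF = 0.288 + 0.199 + 0.081 = 56.7%.

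| 1-KM at 9 months | CIF, PFS 75% | Excess (SE) | CIF, PFS 55% | Excess (SE) |
|---|---|---|---|---|
| 40% | 38.7% | 1.3 (0.21) | 37.4% | 2.6 (0.40) |
| 60% | 58.3% | 1.7 (0.26) | 56.7% | 3.3 (0.50) |
| 70% | 68.3% | 1.7 (0.28) | 66.6% | 3.4 (0.54) |

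With the hazards extrapolated to 18 months, the Case B excess grows to about 4 to 9 points (0.7 to 1.5 SE).

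**The case against.** **The SAP already gives the wanted quantity.** Section 7.5.3 reports the crude percentage of treated patients with grade 3 to 5 toxicity, which does not carry this bias, and the SAP plans no time-to-toxicity curve. This stands and limits the consequence. It does not remove the point, because the SAP does not say that the protocol's analysis is dropped.

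**The censoring rule is inferred.** No rule is written, and Kaplan-Meier could be meant as an on-treatment estimate under independent censoring. It is true that no rule is written. But patients without the event can only be censored under Kaplan-Meier, the planned output includes rates at time points, and no hypothetical estimand is stated. Grade 5 toxic deaths are events and are not in dispute.

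**Toxicity does not become impossible at progression.** A reader might infer that nothing can occur or be counted after treatment stops. The documents do not support that: the window adds 30 days, and related delayed serious events are reportable without limit. Setting the competing event at progression itself would raise the 9-month excess in the 60% row from 5.8 and 11.1 points to 7.7 and 14.7, which ignores the window.

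**The size may be small.** All chemoembolization sessions are scheduled between days 17 and 59, which favours early toxicity and Case B. Against that, FOLFOX continues to progression and Protocol VI.1 lists peripheral sensory neuropathy, so later onset is plausible. Stops for refusal or investigator decision, left out of the model, add further competing events. The documents do not settle which case is nearer.

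**Conclusion.** The point holds as a choice of estimator. As written in Protocol XII.4, the analysis would give a cumulative toxicity rate above the proportion of patients affected whenever death or end of observation comes before the first grade 3 to 5 toxicity. At 9 months the excess is about 5 to 11 points (0.7 to 1.9 SE) under a constant hazard. It is about 1 to 3 points (0.2 to 0.5 SE) if toxicity is mostly in the first 2 months. It grows at later times. These sizes rest on assumed toxicity rates, on independence of toxicity and progression, and on the plan's 55% to 75% range.

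A reader might infer that the excess is material in every case, or that the trial's reported toxicity will be inflated. The documents support neither. Several of the cases above fall below half a standard error, and the SAP's own toxicity tables are crude percentages. The analysis is descriptive, with no test or threshold, and the primary decision is unaffected. The correction should still be made, because the protocol's commitment stands and the two documents differ on whether the analysis exists.

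**What to change.** If the analysis is kept, change Protocol XII.4 and add the analysis to SAP 7.5.3, as follows.
- Estimate the Aalen-Johansen cumulative incidence of first grade 3/4/5 toxicity from first dose, at stated time points, with 95% confidence intervals.
- Take as competing events death without such toxicity, and end of toxicity observation after treatment stop.
- Censor only for data cut-off or loss to follow-up.
- State how related delayed serious events after day 30 are counted.

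If it is not kept, state in the SAP that the time-to-toxicity analysis is dropped in favour of 7.5.3.

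The cost is a few sentences and a standard software option. There is a small downside: cumulative incidence falls when progression is faster. In the 60% row above, the same toxicity hazard gives 68.9% at PFS 75% but 63.6% at PFS 55%, so a less effective regimen looks less toxic. The estimate should therefore be read beside progression-free survival or an on-treatment toxicity rate.
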